3.2. Randomization

Item 10. Randomization details, e.g., whether any minimization or stratification occurred (including stratifying factors used or the location of that information if it is not held within the SAP)

Randomization occurred at school level prior to inclusion of individual participants (i.e., children). A covariate-constrained randomization procedure was carried out to maximize school-level covariate balance between intervention and control group and to increase the probability that child baseline characteristics did not differ substantially between groups.

Allocation was conducted in two strata (1: Western Denmark, i.e. Region of Southern Denmark and 2: Eastern Denmark, i.e. Capital/Zealand Region) and was constrained by the following school-level covariates: Number of children in 1st and 2nd grade, proportion of children with parents of basic educational level (vocational education or lower), proportion of children with non-Danish background, rural or urban municipality, and number of planned weekly physical education lessons. The school-level covariates were obtained from the Ministry of Children and Education (10), and information on physical education lessons was provided by school principals. To ensure timely allocation of schools to their respective groups and allow schools sufficient time to plan the subsequent school year, randomization was conducted in two steps, with the first step based on the first 10 schools recruited, and the second step based on the last 14 schools recruited.

Randomization was performed using the 'cvcrand' command in STATA for covariate-constrained randomization in cluster-randomized trials (11). Randomization was carried out by a statistician not otherwise involved in the study, and the procedure was concealed from the investigators.

Due to the nature of the intervention, the study is open label, i.e. allocation is not blinded to participants, school staff, local communities, or research team members.

After randomization, one control school decided to withdraw from the study, leaving 12 intervention and 11 control schools in the study.

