4.1. Confidence intervals and P values

Item 16. Level of statistical significance

All hypotheses testing will be based on two-sided tests at the alpha = 0.05 level.

Item 17. Description and rationale for any adjustment for multiplicity and, if so, detailing how the type 1 error is to be controlled

No adjustment for multiplicity will be performed.

Item 18. Confidence intervals to be reported

All confidence intervals presented will be 95% and two-sided.

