6.2. Analysis methods

Item 27a. What analysis method will be used and how will the treatment effects be presented

Analysis of *longitudinal the primary outcomes (FM)* will be conducted using a mixed linear regression model. Fixed effects are the time point, the intervention group, the interaction between time point and intervention group, ~~an indicator for the type of measurement used~~, and potential covariates (cf. Item 27b) ~~the covariates mentioned in Item 27b~~. Random effects are school, class, and child specific intercept and slope (with respect to time as a continuous covariate). The covariance matrix of the random intercept and the random slope is allowed to vary freely between the two intervention groups. The error variances are allowed to vary over time and between the intervention groups. ~~The error variance is allowed to vary between ADP and BIA measurements, and a constant difference in variance is assumed~~. The interaction between time point and intervention will be parametrized as time point specific intervention effects. The randomization will be taken into account by restricting the intervention effect at baseline to 0, ~~the difference of the variance of the random intercept between the intervention groups, and the difference in error variances at baseline between the intervention groups to 0~~.

Results of the *primary* analysis will be reported by the effect estimate together with a 95% confidence interval and a p-value of the null hypothesis of no intervention effect based on a Wald test. ~~The treatment effect will be phrased as "difference in mean change between the intervention and control group". In case of using log-transformed outcomes, the treatment effect will be transformed as $(\exp(.)-1)*100$ allowing an interpretation as the "difference in mean percentage change". The boundaries of the confidence interval will be transformed accordingly.~~

The structure of the model:

- Reflects the potential effects of school and classes on the outcome.
- Takes the correlation between measurements from the same child into account.
- ~~Allows using the known association of the primary outcome with height and a potential association with age or sex to increase the power by using them as covariates (if relevant)~~.

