- Allows to include all children from the primary analysis population in the *primary* analysis independent of missing values in the *primary* outcome at some time point (including baseline) – ~~except for those missing the outcome at all time points~~.

- Requires only to assume missing at random (MAR) with respect to missing values in the primary outcome.
- Takes into account the use of two different measurement methods for the primary outcome.

Computations will be based on the default settings of the mixed command in Stata. In case of convergence problems, the complexity of the model will be reduced by the following steps until the convergence is reached: 1) Removal of variance components with estimates on the boundary. 2) Equal error variances across at the two follow up time points. 3) Equal error variances across the intervention groups. 4) Equal correlation between random intercept and random slope across the intervention groups.

The weights (estimated inverse probabilities of participation using register data, described in Item 27b) will be incorporated using the pweight option.

With respect to analyses using both BIA and BODPOD measurements, a corresponding bivariate model will be used (see sensitivity analysis, cf. section 27e). This will require modelling a potential systematic difference between the two measurements.

Item 27b. Any adjustment for covariates

The statistical power of RCTs can be improved by adjusting for (strong) prognostic factors. The approach described above implies already an adjustment for baseline variables. Consequently, there is only a need to adjust for factors which improve the prediction of the outcomes after adjustment for baseline values. Consequently, although FM and some of the secondary outcomes are known to be highly influenced by height, this does not necessarily imply a need to adjust for height.

The decision to adjust for potential prognostic factors will be based on an empirical investigation, whether the prediction of the outcome at the final time point can be improved by adding the factor to a model including the baseline values. Improvements of the adjusted R^2 by at least 0.1 will be regarded as an indicator for inclusion as covariate in the analysis model. The potential prognostic factors considered are height, weight, BMI, age and sex.

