Appendix 1: Rationale for SAP revision, version 2, 18 Nov 2025

1. Scope of changes to SAP

This revision applies to the following items in the SAP:

- 5.5 Baseline characteristics (Item 25b: Baseline characteristics)
- 6.1 Outcome definitions (Item 26b: Measurement methods)
- 6.2 Analysis methods (Item 27a: Analysis method, Item 27b: adjustment for covariates, Item 27e: Sensitivity analyses)
- 6.3 Missing data (Item 28: Handling of missing data)

2. Purpose of this Appendix

This Appendix explains and documents the revision to the primary outcome measurement method and describes the added prespecified sensitivity analyses. The changes are informed by results from the initial data inspection. Note: The initial data analyses were conducted on a dataset without information on allocation – i.e. the analyses were conducted irrespective of allocation to intervention or control group, and without knowledge of the intervention's potential effect on primary or secondary outcomes.

3. Summary of main changes to SAP

In the primary analysis, bioelectrical impedance (BIA) alone will be used to measure fat mass. This replaces the model described in the original SAP, where it was intended to use ADP as the primary measurement, with BIA used only for those with missing data on ADP.

ADP will be used in two pre-specified sensitivity analyses:

- i. An ADP-only analysis: The primary analysis will be repeated using FM measured by ADP at baseline and end-of-study. This analysis will include only participants with a valid ADP measurement, i.e. those wearing standard clothing in the BODPOD.
- ii. A bivariate model combining ADP and BIA at all time-points.

4. Rationale for changes

4.1. Measurement method for primary outcome:

In SAP version 1 (Item 29), we described that we would conduct initial analyses of the impact of clothing on ADP measurements, as it is well-established that non-standard clothing can affect volume estimates during ADP (1). Clothing was recorded during data collection, and clothing was subsequently categorized into three groups:

1. *Standard clothing*, i.e. tight-fitting underwear or swimwear (optimal),
2. *Project clothing*, i.e. clothes provided by the project, which fitted children variably,
3. *Other clothing*, e.g. children's own clothing.

After data cleaning and categorization of clothing, the number of measurements among the 1,359 participants in the analysis population were distributed as follows:

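### Convergence step 1 can remove the school level, and nothing in the SAP then keeps the primary standard error clustered on school, the unit of randomization

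*SAP*

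**What the plan says.** Section 3.2 makes school the unit of allocation: "Randomization occurred at school level prior to inclusion of individual participants". One control school withdrew, "leaving 12 intervention and 11 control schools in the study". Section 4.1 sets the standard: "All hypotheses testing will be based on two-sided tests at the alpha = 0.05 level".

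The primary model is in section 6.2, Item 27a: "Random effects are school, class, and child specific intercept and slope (with respect to time as a continuous covariate". The sentence does not settle whether only the child, or also the school and class, has a slope on time. The primary result is a Wald test of the difference in change in fat mass. On software, the SAP says: "Computations will be based on the default settings of the mixed command in Stata". Participation weights enter through pweight. Neither the type of standard error nor the degrees of freedom is named.

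If convergence fails, four simplifications are tried in order. The first is "1) Removal of variance components with estimates on the boundary". The other three concern only the error variances and the correlation between random intercept and slope.

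**The concern.** The comparison rests on 23 randomized schools, so the standard error has to carry the variation between schools in how fat mass changes. As written, that protection rests on a software default that the SAP does not state, and it lasts only while school is the top level of the model.

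Step 1 can take that level out. On the better-supported reading, the component removed is the school variance in fat mass level, whereas the tested effect is on change. Schools may have nearly equal average levels and still differ in change, particularly when the intervention is delivered through schools. With school gone, the robust standard error would treat classes as independent, and a null intervention could be declared effective more often than the stated 5%. A pre-specified rule would have produced that result, so it would be hard to challenge afterwards.

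Step 1 also comes before the simplifications of the error variances and the correlation. Trouble in the child part of the model can therefore lead to removal of the school component first. Per arm, that part has three intercept and slope parameters plus three error variances, for the six variances and covariances of three visits, so convergence difficulty is plausible.

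**Working it through.** The SAP states no intraclass correlation, standard deviation or power (section 3.3 refers to the protocol), so there is no figure to reproduce.

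**Inputs from the SAP**
- Schools: 12 + 11 = 23 (section 3.2), so 23 − 2 = 21 degrees of freedom between schools.
- Bioimpedance measurements at end-of-study: 1,197 (Appendix 1, Table S1), so m = 1,197/23 = 52.04 per school.

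**Assumptions**
- School intraclass correlation of change, ρ: 0.01 to 0.03.
- Four classes per school with 13 children each.
- mixed with pweight gives robust standard errors clustered on the highest level in the model.

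**1. Error if school is lost and clustering falls to class.** The true variance is inflated by 1 + (m − 1)ρ. Class clustering captures only 1 + (13 − 1)ρ. Error = 2[1 − Φ(1.96/√ratio)].

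| ρ | 1 + 51.04ρ | 1 + 12ρ | ratio | two-sided error |
|---|---|---|---|---|
| 0.01 | 1.51 | 1.12 | 1.35 | 9.1% |
| 0.02 | 2.02 | 1.24 | 1.63 | 12.5% |
| 0.03 | 2.53 | 1.36 | 1.86 | 15.1% |

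A simulation of this layout (4,000 runs per setting, two visits) gave 9.8% to 16.5%. Restricted to runs with a zero school intercept variance, it gave 9.2% to 18.0%. A second simulation (2,000 runs, 15 children per class, three visits, school level dropped) gave 10.7% at ρ = 0.01 and 13.0% at ρ = 0.02.

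**2. Error with school-clustered standard errors.** With t on 21 degrees of freedom, the first simulation gave 5.0% to 6.2% and the second 4.3% to 6.1% (ρ from 0 to 0.05). With a normal reference the second gave 5.4% to 7.7%. For comparison, a t variable on 21 degrees of freedom exceeds 1.96 in absolute value 6.3% of the time. This is why a small-sample reference belongs in the fix.

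**3. Chance of a zero school estimate when the true variance is not zero.** In a one-level analysis of variance this is P(χ²₂₁ < 21(1 − ρ)/(1 − ρ + mρ)), where ρ is now the school correlation of fat mass level.
- ρ = 0.005: P(χ²₂₁ < 16.65) = 27%.
- ρ = 0.01: P(χ²₂₁ < 13.76) = 12%.
- ρ = 0.02: P(χ²₂₁ < 10.18) = 2.4%.
- ρ = 0.03: P(χ²₂₁ < 8.05) = 0.5%.

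This is the chance of a boundary estimate, not of a convergence failure. Both are needed.

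**4. If standard errors were model-based instead, with a slope for the child only.** School variation in change would then be missing from the start. Error = 2[1 − Φ(1.96/√(1 + 51.04ρ))] = 11.1%, 16.8% and 21.8% at ρ = 0.01, 0.02 and 0.03. Step 1 itself would do no harm here: removing a component already estimated at exactly zero leaves the fit and the standard error unchanged.

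**The case against.** The strongest reply is that the plan as specified does respect schools. It uses pweight. If that brings robust standard errors clustered on the top level, between-school variation in change is covered even without a school slope. In the second simulation, with school kept and no school slope, error was 5.4% to 7.6% against a normal reference for ρ from 0.01 to 0.05. This stands. A reader might infer that the primary standard error, as planned, already omits schools. The document does not support that, and the 11% to 22% figures do not describe the planned analysis under this assumption.

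The wording on slopes is also open. The singular references to one random intercept and one random slope favour a child-only slope but do not exclude slopes at every level. If schools do have slopes, both the school intercept and the school slope would have to be removed before the level disappears.

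The risk is conditional on a convergence failure together with a boundary school estimate. The second is uncommon if fat mass level has a school correlation of 0.02 or more. Nor do the simulations reproduce the stratified, covariate-constrained allocation, so the error rates are indicative. These points lower the severity.

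They do not close the gap. Nothing says that clustering on school survives step 1. The leave-one-school-out analysis checks the influence of single schools and does not supply a school-level standard error.

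**Conclusion.** The point holds as a conditional weakness of the fallback rule. If the model fails to converge and the school component is on the boundary, following Item 27a literally can leave a primary test clustered on class. Its error would be about 9% to 18%, against about 5% to 6% with school clustering and t on 21 degrees of freedom. This rests on an assumed school correlation of change of 0.01 to 0.03, an assumed class layout, and the stated assumption about Stata's robust standard errors. If standard errors were model-based and the slope child-only, error would be about 11% to 22% without any fallback.

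How often the fallback would be used cannot be worked out from the SAP, so no overall error rate for the trial follows from these figures. Severity: should be fixed before the effect analyses are run.

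**What to change.** In Item 27a, state that:
- standard errors are clustered on school in every fit of the continuous-outcome models (primary, secondary, sensitivity and all fallback models), whichever random effects remain;
- tests and intervals use a small-sample reference, such as t on about 21 degrees of freedom;
- the time slope is carried by the named level or levels.

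A school component estimated at zero may be set to zero under step 1, provided that clustering on school stays. A school-level random slope is optional. It is not needed once standard errors are clustered on school, and it would add complexity to a model that may already be hard to fit.

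The cost is a few sentences in the SAP and a clustering option in the code, with the t reference applied to the estimate and its standard error. Intervals may become somewhat wider. Outcomes, data and the estimated effect stay as they are.

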We selected FM as our primary outcome because the intervention targets four behavioural components (diet, physical activity, screen media use, and sleep) which may all affect FM. In contrast, other aspects of body composition, in particular fat free mass (FFM), is only expected to be affected by the physical activity component. FM was considered a more appropriate primary outcome than weight-based measures (e.g. BMI z-score), because certain intervention components, particularly physical activity, may increase FFM (15), while e.g. the diet intervention may reduce FM. Such beneficial effects on body composition would not be reflected in changes in overall weight-based measures. Therefore, favourable intervention effects could be masked by using weight-based measures as the primary outcome.

We used FM in power calculations instead of FM index (2), because we anticipated that due to the cluster-randomized design, height would be equally distributed across intervention and control groups.

Measurement method for primary outcome:

The primary outcome is assessed by two measurement methods:

- 1) *Air-displacement-plethysmography (ADP) (BODPOD)*. This method has demonstrated a level of agreement with the 4-compartment model comparable to that of dual-energy X-ray absorptiometry in children **with obesity** (16). For logistical and resource reasons, ADP was only applied at baseline and end-of-study
- 2) *Bioimpedance analyser (BIA) (InBody 270)*. BIA is a highly feasible field method for estimating body composition, but it has shown lower agreement than ADP with the gold-standard 4-compartment model **in children with obesity** (16). The BIA method was applied at all three time points.

For the present study, we assume ADP to be the more accurate measurement (16), and the ADP results will therefore be used whenever available. BIA will only be used if no ADP measurement is available, i.e. for children with missing data on ADP at baseline or end-of-study, and for the measurements at the interim time point. Furthermore, as the ADP results are sensitive to the child's clothing, BIA results will be used if a child did not wear the same clothes (e.g. swimwear, light clothing) at baseline and end-of-study.

In the primary analysis of FM, we will use BIA data. ADP measures of FM will be used in pre-specified sensitivity analyses (See item 27e). Further details on reasons for this change are provided in Appendix 1 to this SAP.

Secondary outcomes:

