The distribution of any variable included in any later analysis will be depicted graphically in the overall population and stratified by age and sex. Time varying variables will be also stratified by time point of assessment, and the analysis will be extended to change scores, i.e. differences from baseline to follow-up.

Outliers will be identified visually, and data will be checked for potential explanations. In case of explanations indicating an undue effect of external factors, outliers might be removed. Any decision of this kind will be documented and included in the supplementary material of the paper.

Consistency checks of individual trajectories

For each longitudinal outcome, the individual longitudinal trajectories of each child will be inspected with respect to a uniform development. Suspicious measurements will be checked.

Check of expectations

The outcomes considered in this study are well-established. Population norms are available and associations with child characteristics are well-established. The distribution of these variables and their association with child characteristics in this study at baseline will be depicted and compared with data from the literature, for example national data on prevalence of childhood overweight and obesity (5), to establish the validity of the measurement methods and evaluate the representativeness of the study sample.

Item 27d. Details of alternative methods to be used if distributional assumptions do not hold, e.g., normality, proportional hazards, etc.

In case of skewed distributions or other anomalies, potential data transformations will be discussed, or additional sensitivity analyses will be defined.

Item 27e. Any planned sensitivity analyses for each outcome where applicable

To evaluate the robustness of our results to the method used to measure body composition, two sensitivity analyses will be conducted:

1. An ADP-only analysis: The analysis will be repeated using FM measured by ADP at baseline and end-of-study. This analysis will include only participants with a valid ADP measurement, i.e. those wearing standard clothing in the BODPOD.
2. A bivariate model combining ADP and BIA measurements at all time-points: This model will include up to five measurements of FM per child (ADP and BIA at baseline, BIA at interim, ADP and BIA at end-of-study).

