| | Baseline | | Interim | | End-of-study | |
|-----------------------|--------------|------------|--------------|------------|--------------|------------|
| | n | % | N | % | n | % |
| ADP available | 909 | 67 | NA | - | 1,039 | 76 |
| Clothing 1 (standard) | 587 | 43 | NA | - | 708 | 52 |
| Clothing 2 (project) | 204 | 15 | NA | - | 231 | 17 |
| Clothing 3 (other) | 118 | 9 | NA | - | 100 | 7 |
| BIA available | 1,274 | 94 | 1,225 | 90 | 1,197 | 88 |
| Total | 1,359 | 100 | 1,359 | 100 | 1,359 | 100 |

Table S1. Number of measurements of primary outcome across measurement methods, measurement rounds and ADP clothing categories.

Table S1 shows that the total number of ADP measurements is substantially lower than the number of BIA measurements. A notable proportion of children declined the ADP assessment because they found the BODPOD intimidating.

In our efforts to investigate the impact of clothing, Bland–Altman plots stratified by clothing category and height were generated to assess agreement between BIA and ADP. These plots indicated that agreement varied systematically with both clothing category and child height (see Figure S1). These findings highlighted the impact of clothing, leading us to consider only clothing category 1 as valid. Consequently, less than half of participants had valid ADP measurements at baseline (43%) and approximately half at end-of-study (52%) (Table S1).

Bland-Altman plots by height/clothing

[figure not shown]

Figure S1: Bland–Altman plots showing agreement in fat mass between air-displacement plethysmography (ADP; fmbodpod) and bioelectrical impedance analysis (BIA; fmbia), stratified by clothing category (1, 2, 3) and height (120, 130, 140, 150 cm).

Given i) the considerable numbers of children with missing data on ADP under the validity restriction concerning clothing; and ii) the systematic differences between ADP and BIA related to clothing and height, we decided that the primary analysis of the intervention effect on FM will only include BIA measurements.

To be completely transparent and to examine the robustness of the study results on the selection of measurement method for the primary outcome, we will include two pre-specified sensitivity analyses:

- i. An ADP-only analysis: The primary analysis will be repeated using FM measured by ADP at baseline and end-of-study. This analysis will only include the participants with a valid ADP measurement, i.e. those wearing standard clothing in the BODPOD.

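### The ADP-only sensitivity analysis changes the children as well as the instrument, so a result that differs from the BIA analysis could not be attributed to the measurement method

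*SAP*

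**What the plan says.** SAP section 6.1 fixes the instrument for the primary outcome: "In the primary analysis of FM, we will use BIA data". On visits it adds: "The BIA method was applied at all three time points". ADP was used only at baseline and end-of-study.

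Section 6.2, Item 27e, gives the purpose of the two added analyses: "To evaluate the robustness of our results to the method used to measure body composition, two sensitivity analyses will be conducted". The first is described as follows: "The analysis will be repeated using FM measured by ADP at baseline and end-of-study". Its population is then restricted: "This analysis will include only participants with a valid ADP measurement, i.e. those wearing standard clothing in the BODPOD". The second is a bivariate model with up to five fat mass values per child. Item 27a notes that this model must allow for a systematic difference between the two methods.

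Appendix 1, section 4.1, counts the readings in Table S1 and explains part of the shortfall in ADP: "A notable proportion of children declined the ADP assessment because they found the BODPOD intimidating". Section 6.4 (Item 29, initial data analyses) gives the child's choice as the reason for not correcting volumes for clothing. Section 2.3, secondary objective 2A, expects that the intervention effect may depend on adiposity at baseline.

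**The concern.** A check of robustness to the instrument should change the instrument and hold the children fixed. Here both change. The ADP-only set consists of children who agreed to enter the BODPOD and wore standard clothing, so it is self-selected. If these children differ in adiposity from the rest, and the effect varies with adiposity as the SAP thinks possible, the ADP-only estimate can differ from the BIA estimate even if both instruments give the same effect in every child.

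At stake is how to read this check. Version 2 of the SAP made BIA the primary method, although section 6.1 reports that BIA agreed less well than ADP with the four-compartment reference in children with obesity. Appendix 1 presents the two sensitivity analyses as the way to show whether results depend on that choice. A discrepancy would have two competing explanations, and the plan has no comparison that separates them.

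**Working it through.** **Inputs (Appendix 1, Table S1).** The denominator is given by "the number of measurements among the 1,359 participants in the analysis population were distributed as follows".

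- Standard-clothing ADP: 587 at baseline, 708 at end-of-study.
- BIA: 1,274 at baseline, 1,225 at interim, 1,197 at end-of-study.

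**Step 1: reproduce the plan's percentages.**

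- Valid ADP: 587/1,359 = 43.2% and 708/1,359 = 52.1%, stated as 43% and 52%.
- BIA: 1,274/1,359 = 93.7% and 1,197/1,359 = 88.1%, stated as 94% and 88%.

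**Step 2: size of the ADP-only set.** Children without a valid ADP reading number 1,359 − 587 = 772 at baseline and 1,359 − 708 = 651 at end-of-study. The SAP does not say whether a child needs a valid reading at one visit or both.

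- Both visits required: between max(0, 587 + 708 − 1,359) = 0 and min(587, 708) = 587 children. If validity at the two visits is assumed independent, about 587 × 708/1,359 = 306 (23%).
- One visit sufficient: between 708 (52%) and 587 + 708 = 1,295 (95%) children.

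Under either rule, at most 708 children supply an end-of-study ADP value.

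**Step 3: how far selection alone could move the estimate (illustration).** Assume that both instruments give the same effect in any given child. Let f be the ADP subset's share of the population and r the effect in the subset divided by the effect in the other children. Then ADP-only estimate / full-population estimate = r / (f·r + 1 − f).

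| f | r = 0.5 | r = 2 |
|---|---|---|
| 0.23 (306 children) | 0.56 | 1.63 |
| 0.43 (587 children) | 0.64 | 1.40 |
| 0.52 (708 children) | 0.68 | 1.31 |

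The SAP gives no value for r; 0.5 to 2 is an assumed range. Within it, the two estimates differ by a factor of 0.56 to 1.63 with no method difference at all.

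**Step 4: how far chance alone could move it.** Assume a random nested subset, independent children and equal precision per child. The SD of the difference between subset and full estimates is then √(1/f − 1) times the full-sample standard error: 0.96 for f = 0.52, 1.15 for f = 0.43 and 1.86 for f = 0.23. So a gap of about one full-sample standard error or more would be unremarkable. Comparing instruments within the same children removes this sampling difference.

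**Step 5: does another planned analysis close the gap?**

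- Complete-case analysis (Item 27e): defined by completeness of the considered outcome at all time points, not by ADP validity.
- Drop-out description (section 6.4): names ADP, BIA and missing as availability levels, but the variable to be tabulated by arm subdivides missing BIA. It does not mention clothing validity, and a tabulation gives no effect estimate.
- Bivariate model (Items 27a and 27e): uses both instruments, but the SAP does not say that it gives an intervention effect per method, or that its ADP values are limited to standard clothing.

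**Step 6: size of a matched set.** BIA is missing for 1,359 − 1,274 = 85 children at baseline and 1,359 − 1,197 = 162 at end-of-study. Readings with both methods therefore number 587 − 85 = 502 to 587 at baseline and 708 − 162 = 546 to 708 at end-of-study.

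**The case against.** The strongest reply is that the two sensitivity analyses belong together. A bivariate model with BIA on nearly all children lets BIA inform the missing ADP values under missing at random, which is a recognised way to handle a self-selected subset. This stands in part: the model could partly separate method from selection if it gave method-specific effects and used only valid ADP. The SAP specifies neither, and the model does not change what the ADP-only analysis can show by itself.

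A reader might infer that the switch to BIA rests on this check. The documents do not support that. Appendix 1, section 4.1, bases the switch on the amount of missing valid ADP and on disagreement related to clothing and height. The switch was decided without allocation information and before any effect analysis.

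A reader might also infer that ADP validity is known to depend on body size or arm. The SAP documents refusal and the child's choice of clothing, in an open-label trial; dependence on body size or arm is a plausible risk, not a documented fact.

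The analyses also differ in visits (three against two). This is minor and unavoidable: ADP was not used at interim, and both analyses target change from baseline to end-of-study.

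**Conclusion.** The point holds for attribution. As planned, the ADP-only analysis changes instrument and children together, and no planned analysis applies BIA to the ADP-valid readings. A discrepancy could not be assigned to the instrument. It would be too strong to call the analysis uninformative: agreement would still be some reassurance, although offsetting differences remain possible.

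The counts (43% and 52% valid ADP) come straight from Table S1. It would also be too strong to say that at most 587 children can enter the ADP-only analysis, since that ceiling applies only if both visits are required. The range of 0.56 to 1.63 is an illustration resting on the assumed r and f, not an estimate of bias. The primary BIA estimate is unaffected. The gap concerns the interpretation of a sensitivity analysis, but it is worth closing because closing it is nearly free.

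**What to change.** Add to Item 27e: *The ADP-only analysis and a BIA analysis will both be run, with the same model, on the baseline and end-of-study child-visits that have both a valid standard-clothing ADP reading and a BIA reading.* Compare ADP with matched BIA for the method effect, and matched BIA with full-set BIA for the effect of the restriction. State whether valid ADP is needed at one visit or both, and report ADP-valid counts by arm.

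The shared model must be one that two visits can support. Item 27a's child-level structure has five parameters per arm (intercept variance, slope variance, their covariance and two error variances), whereas two visits give three distinct variance and covariance elements. Whatever reduction is made should be the same for both instruments.

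Cost: one or two extra runs on data already held, with no change to the primary analysis. The matched set is smaller, so its precision is limited and its results should be read with their confidence intervals.
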